## **2.8 Participant privacy and confidentiality**

The investigator affirms and upholds the principle of the participant's right to privacy and that they shall comply with applicable privacy laws. Especially, anonymity of the participants shall be guaranteed when presenting the data at scientific meetings or publishing them in scientific journals.

Individual subject medical information obtained as a result of this study are considered confidential and will not be disclosed to third parties. Subject confidentiality will be further ensured by the use of code numbers in all collected data.

For data verification purposes, authorised representatives of the Sponsor or of the CER-VD may require direct access to parts of the medical records relevant to the study, including participants' medical history.

## **2.9 Early termination of the study**

The Sponsor-Investigator may terminate the study prematurely if the NHs where the study takes place express concerns regarding the safety of the participants. The CER-VD will be informed within 15 days in case of premature termination.

## **2.10 Protocol amendments**

Substantial amendments proposed by the sponsor or investigators will only be implemented after approval of the CER-VD.

Under emergency circumstances, deviations from the protocol to protect the rights, safety and well-being of human subjects may proceed without prior approval of the sponsor and the CER-VD. Such deviations will be documented and reported to the sponsor and the CER-VD as soon as possible.

All non-substantial amendments will be mentioned in the final report to the CER-VD.

### 3. BACKGROUND AND RATIONALE

#### 3.1 Background and Rationale

Polypharmacy, or the use of five or more concurrent medications, is frequent among the elderly [3], and especially those residing in NHs [4]. While appropriate in many cases, especially when multiple concurrent drugs are required to adequately treat a health condition, for example diabetes, polypharmacy has been shown to increase the risk of adverse drugs events (ADE) [5] and may lead to decreased health outcomes and quality of life [6].

Inherent risks posed by polypharmacy are amplified by the use of potentially inappropriate medications (PIMs), drugs whose potential for harm surpass their expected benefits [7]. PIMs have been a major concern for the geriatric care community since the early 1990s, with the publication of Beers' seminal paper [8]. Their use is associated with worse health outcomes, more frequent hospitalisation and increased risk of death [9, 10]. Elderly people residing in NHs are frequently exposed to such drugs: a meta-analysis by Morin et al [11] found that at least 43% of NH residents worldwide receive at least one PIM each year; in Europe, this figure goes up to 49%. A study conducted by the Helsana health insurance showed that Swiss NH residents are not better off than their European counterparts: at least 45% of NH residents insured by Helsana receive at least one PIM every quarter [12].

In the past years, the concept of deprescribing emerged in the literature as a potential way to address both polypharmacy and PIMs. Defined as "the process of withdrawal of an inappropriate medication, supervised by a health care professional with the goal of managing polypharmacy and improving outcomes" [13], deprescribing has the potential to improve elderly people's well-being and health outcomes [14]. A recent meta-analysis indeed concluded on the positive effect of patient-centred deprescribing intervention on mortality [15]. Since the first occurrence of the term in the scientific literature [16], deprescribing has gathered interest in various countries, such as Australia [17], Canada [18], the United States [19], New Zealand [20], Belgium [21], the Netherlands [22, 23], and France [24]. Outside of the academic world, deprescribing is also gaining traction, with initiatives such as guidelines published by the Canadian Deprescribing Network [25] or the MedStopper online tool [26].

In Switzerland, preoccupations relative to the medication regimen of NH residents are present as well: the not-for-profit organisation *patient safety switzerland* launched, in 2016, an initiative called *progress! La sécurité de la médication en EMS* (Drug safety in NH) [27]. This initiative led to the publication in 2018 of a preliminary report highlighting the need for concrete solutions to be investigated regarding polypharmacy and the use of inappropriate medications by NH residents [28]. To our knowledge, however, apart from the QC-DeMo study (see below), no initiatives have been launched to try to implement deprescribing in the Swiss NHs. One of the reasons could be that, to be successful, deprescribing must rely on interprofessionnal collaborations [29] that may not be as developed in Switzerland as in other countries. Such collaborations do however exist locally in Switzerland: since 2002 in the canton of Fribourg [30] and 2010 in the canton of Vaud, pharmaceutical assistance programmes (PAP) are in place in the NHs of those cantons. These programmes consist of interprofessional quality circles bringing together physicians, nurses and pharmacists on a regular basis, to improve medications prescribing and use in the NH through the building of local treatment consensus. These existing and successful, local collaborations are an opportunity to develop deprescribing in the Swiss NHs.

This study takes part in a larger research program entitled "Opportunities and Limits to Deprescribing in Nursing Homes" (OLD-NH), funded by the Swiss National Fund for Scientific Research, through the National Research Programme 74 "Smarter Health Care" [31]. The OLD-NH program started with a first phase consisting of two qualitative studies exploring the context surrounding the withdrawal of medications in the Swiss NHs. The first study was focused on the professionals' point of view (protocol submitted to the CER-VD in 2016 and declared as out of the HRA's scope), and the second on the NH residents' perspectives (protocol 2017-00211 accepted on 10.04.2017 by the CER-VD). Both these studies have been completed and their results informed the design of the present study.

The second phase of OLD-NH consists of two interventional studies; the first one, OLD-NH-QC-DeMo, is ongoing (protocol submitted to the CER-VD in 2017 and confirmed as out of HRA's scope, Req-2017-01009). This first study is a RCT of a Quality Circle Deprescribing Module (QC-DeMo), in which participating NHs allocated to intervention held an interprofessional quality circle bringing together nurses, pharmacists and physician, with the goal of defining a local deprescribing consensus focused on the most widely used PIMs. The physicians were then free to implement or not the deprescribing consensus in residents receiving the targeted PIMs, based on their clinical judgement.

The study described in this protocol is the second in the intervention phase of OLD-NH. It aims to test the effects of an additional intervention in the NHs who already held the QC-DeMo intervention and implemented the deprescribing consensus.

### **3.2 Intervention to be investigated**

The intervention investigated is a pharmacist-led medication review, focused on the deprescribing of inappropriate medications, resulting in the creation, validation and application of an individual deprescribing plan by the NH care team.

After performance by the pharmacist, the results of the medication review will be discussed with the clinical staff of participating NHs (pharmacist, treating physician, and head nurse), with the goal of producing a treatment modification plan tailored to the needs of each participant (deprescribing plan). The deprescribing plan will then be discussed with the participant or her/his representative before being enacted.

Details of the intervention are presented in section 8 (page 20).

### **3.3 Preclinical Evidence**

Not applicable to this study.

### **3.4 Clinical Evidence to Date**

Deprescribing has already been shown to be an effective way to reduce the number of drugs used by older people living in NH: an Australian study randomised 95 participants to a deprescribing intervention or usual care [32]. Participants in the intervention group received a lower number of drugs ( $-2.0 \pm 0.9$ ) 12 months after intervention than participants in the control group. This reduction did not increase mortality, falls or hospital admissions, and did not negatively influence cognitive functions, quality of life or sleep.

A 2016 systematic review found that deprescribing could be safely enacted in older people [15]: in randomised trials, individual deprescribing interventions led to a lower mortality, without lowering cognitive functions, increasing the risk of falls, or increasing the occurrence of adverse events.

Studies indeed show that enacting deprescribing induces very little acute adverse events: in a study of deprescribing in 422 NH residents in the United Kingdom [33], only seven adverse events occurred following the discontinuation of more than 700 medicines. None of those seven events led to significant harm to the residents; the measures taken to resolve these events included the reinstatement of the stopped medication, the treatment of a urinary tract infection, the adaptation of an insulin regimen, and closer monitoring of blood pressure. In the previously cited trial of deprescribing in Australian NHs [32], there were no differences in the occurrence of adverse events between the intervention and control groups.

These findings were confirmed by a recent study of deprescribing in Dutch NHs residents [23]: reducing the number of medication prescribed to 159 NH residents did not worsen their clinical condition or their quality of life, compared to 193 residents which were not subject to the deprescribing intervention.

In case of acute adverse reaction after the withdrawal of a drug, corrective measures, including reinstating the treatment, can be put into practice extremely quickly given the close monitoring of residents in NHs. The risks of stopping long-term preventive treatments (for example cholesterol-lowering drugs) are less well known; however, the benefits of such preventive drugs in the very elderly are also not well established: most preventive drug have not been studied in this population [6]. The benefits of these treatments in the adult population are, in general, expected to occur in a timeframe longer than the average life expectancy of NH residents: the mean duration of stay in the NHs of Fribourg and Vaud was less than 3 years in 2015 [34].

### **3.5 Dose Rationale**

Not applicable to this study.

### **3.6 Explanation for choice of comparator**

The intervention will be compared to usual care: participants affected to the control group will still benefit from the interprofessional collaboration already in place, including the effects of the deprescribing consensus resulting from the NH's participation in OLD-NH-QC-DeMo (see page 9).

This comparator was chosen because the goal of this study is to investigate the effects of an individual deprescribing intervention following the NH-wide approach evaluated in the QC-DeMo study, from which residents of the whole NH benefit.

### **3.7 Risks / Benefits**

As discussed previously (see section 3.4 before), deprescribing inappropriate medication lead to few adverse events and does not worsen the clinical condition or quality of life of older people; it can also lead to a reduction in mortality.

In addition to these reassuring results from the literature, the participants' treating physicians will remain in complete control of their treatment (see section 8.1.1, page 20). The risks incurred by residents taking part in this study is thus deemed minimal, and no greater than usual care.

No threat to the study (competing trial, change in the regulatory framework, or otherwise) is anticipated.

### **3.8 Justification of choice of study population**

Older people living in NHs were chosen as study population because of the high number of drugs they receive and the high rate of PIMs use [35] among them, which make them more likely to benefit from a deprescribing intervention. In addition, the good collaboration already in place between physicians, nurses, and pharmacists in the NHs taking part in the QC-DeMo study provide an ideal ground to implement deprescribing at an individual level.

The broad inclusion criteria (see section 7.1, page 19) for this study imply the possibility that NH residents incapable of judgement because of cognitive impairment, for example suffering of dementia, will be included in the study. These residents are amongst the most vulnerable, but their inclusion is essential to the conduct of this study, as they constitute a large proportion of the NH population: in Europe, over 60% of NH residents exhibit cognitive impairment [36], and it is estimated that 2/3 of residents in Swiss NHs are affected by a dementia-like pathology [37]. While the proportion of residents with cognitive impairment is not precisely known in Vaud or Fribourg, the last available statistics on the subject indicate that at least 40% of NH residents are diagnosed with a dementia [38]. In 2016, 42% of NH beds in Vaud were in institutions with a psychogeriatric mission [39]. No data are available for the canton of Fribourg, but we have no reason to believe that the situation is different. Excluding residents presenting a cognitive impairment would greatly reduce the external validity of the findings of this study, thus limiting their transferability.

For cognitively impaired residents, their legal representative will have to consent to participation. Representatives will be contacted directly by the NH team and be given the same explanations as NH residents capable of judgement (see section 7.2, page 19 and Annex 1). A specific information and consent form has been prepared for this situation (Annex 2).

We have a priori no idea of how eligible residents with cognitive impairment rendering them unable to communicate could express their disagreement to participate to the study. However, their cognitive state will be taken into account by the healthcare team and their representative to validate their participation, and to establish the deprescribing plan. In case of deprescribing, any sign of discomfort or symptoms related to the withdrawn drug will be addressed and the reintroduction of stopped drugs remain possible at any time.

## **4. STUDY OBJECTIVES**

### **4.1 Overall objective**

The purpose of this study is to evaluate the effects of a deprescribing intervention, a pharmacist-led, deprescribing-focused medication review followed by the creation of a deprescribing plan with the NH care team, on the use of PIMs in select NHs, as well as its implementation. The study will be conducted in NHs included in the intervention arm of the OLD-NH-QC-DeMo study (see section 3.1, page 13), as the effects of the intervention tested here is cumulative with the deprescribing intervention tested at the NH level in the QC-DeMo study.

### **4.2 Primary objective**

This study seeks primarily to determine the effect of the intervention on the number of PIMs used by NH residents, compared to usual care.

### **4.3 Secondary objectives**

Secondary objectives are to evaluate the effects of the medication review on the participants' health-related quality of life and the prevalence of common complaints related to drugs frequently used by elderly people.

#### **4.4 Implementation objectives**

Implementation objectives are to assess the acceptability, adoption, feasibility, appropriateness, penetration, fidelity, sustainability and costs of the intervention.

#### **4.5 Safety objectives**

This study aims to assess the safety of the deprescribing intervention in terms of mortality, hospitalisation, falls and the use of restraints.

### **5. STUDY OUTCOMES**

#### **5.1 Primary Outcome**

The primary endpoint of the study is the change in the number of PIMs prescribed to participants between baseline and 4 months. It was chosen because the main effect of the intervention will be to reduce the number of inappropriate medications prescribed to participants.

#### **5.2 Secondary Outcomes**

Secondary outcomes are:

1. The change between baseline and 4 months in the number of potentially inappropriate Defined Daily Doses (DDDs) prescribed to participants;
2. The change between baseline and 4 months in the number of regular drugs prescribed to participants;
3. The change between baseline and 4 months in the number of regular DDDs prescribed to participants;
4. The number of new drugs prescribed as a result of the intervention;
5. The change in health-related quality of life between baseline and follow-up, measured with EQ-5D-5L [40] (see Annex 4 for the questionnaires);
6. The change in the number of common drug-related complaints presented by the participant between baseline and follow-up (see Annex 5 for the questionnaire on common complaints);

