# **8. STUDY INTERVENTION**

## **8.1 Identity of Investigational Intervention**

### **8.1.1 Experimental Intervention**

The intervention tested in this study is a medication review focused on deprescribing, followed by the construction and implementation of a deprescribing plan. A medication review is "a structured evaluation of a patient's medicines with the aim of optimising medicines use and improving health outcomes." [48] This review will take into account the clinical situation of the participant, including pathologies, disabilities, current drug regimen, and her / his therapeutic and life goals.

The responsible pharmacist of the NH where the participant resides will perform the medication review. They will receive education on the realisation of medication review prior to the study by attending the "Medication review" module of the Certificate in Advanced Studies "Pharmacie Clinique: prestations dans les soins de base" . Through the study, pharmacists will be able to solicit the clinical advices of the *Centre de Pharmacie Communautaire* Pharmaceutical Assistance team for performing of the reviews.

The results of the review will be structured propositions of drug regimen modification, according to the clinical situation of participant and the risk/benefit balance of each prescribed drug for her-/him-self. These propositions will include regimen modifications (modification of galenic forms or administration time or frequency), withdrawal or tapering of non-beneficial drugs (deprescribing), and introduction of new drugs in case of prescribing omission (sub-optimal treatment). These propositions will be discussed with nurse and treating physician of the NH, with the goal to create a deprescribing plan that will be proposed to the participant. The propositions resulting from the review and the deprescribing plan will be prepared following the model documents in Annex 8.

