### **8.1.2 Comparator**

The comparator will be usual care, as routinely provided in the NHs where the study takes place.

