### **8.6 Trial specific preventive measures**

All interventions part of usual care deemed necessary by the NH care team are allowed before and during the trial, in both arms. Specifically, modifying or stopping a treatment is allowed in the patients allocated to the control group, and restarting a withdrawn treatment is allowed in the intervention group.

The interventions other than the ones specified in the deprescribing plan will not be collected, as they are of no interest to the study outcome and would impose too big a workload on the NHs care team.

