## 9.2.3 Assessment of implementation outcomes

### 9.2.3.1 *Number and rate of pharmacist propositions validated by the care team, of validated propositions accepted by the participants, and of accepted propositions implemented within 4 months.*

Those 6 outcomes will be computed from the information provided on the deprescribing plans at baseline and follow-up.

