#### 11.4.2 Descriptive statistics

The participants will be described, by group, in terms of age, gender, and length of stay in the NH at inclusion. Their drug regimen at baseline and follow-up will be described in terms of number of regular treatments, classified according to the Anatomical Therapeutic Chemical classification. Drugs withdrawn or added as a result of the intervention will be described in the same way.

Implementation outcomes will be analysed in descriptive terms only; no statistical tests will be performed on these data.

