#### 11.4.4 Secondary Analyses

The same GLMM models as for the primary outcomes will also be used to compare all patient-level secondary outcomes between the intervention groups. NH-level outcomes will be compared between allocation groups by mean of t-tests if the outcomes follow a normal distribution, by means of Mann-Whitney otherwise.

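### Secondary outcome 4 can be non-zero only in the intervention arm by its own wording, yet section 11.4.4 does not exempt it from the between-arm comparison and section 9.2.2 gives it no derivation

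*Combined protocol and SAP*

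**What the plan says.** Section 5.2 defines the fourth of six secondary outcomes as "The number of new drugs prescribed as a result of the intervention".

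New drugs are a recognised product of the intervention. Under section 8.1.1 the pharmacist's propositions may include "introduction of new drugs in case of prescribing omission (sub-optimal treatment"), and section 6.1 carries these into the deprescribing plan. Section 6.1 makes that plan only for participants allocated to intervention. For controls, section 8.1.2 states: "The comparator will be usual care, as routinely provided in the NHs where the study takes place".

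Section 11.4.4 sets the analysis: "The same GLMM models as for the primary outcomes will also be used to compare all patient-level secondary outcomes between the intervention groups". NH-level outcomes go to a t-test or Mann-Whitney test between the same groups. No secondary outcome is excepted.

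Section 11.4.2 contains two relevant sentences. One concerns this quantity: "Drugs withdrawn or added as a result of the intervention will be described in the same way". The other is an explicit exemption from testing, but for a different list: "Implementation outcomes will be analysed in descriptive terms only; no statistical tests will be performed on these data".

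**The concern.** A between-arm comparison needs a quantity that either arm could have. Outcome 4 carries the cause in its definition: a drug counts only if the intervention led to it. A control resident who starts a drug under usual care does not qualify, and no rule says how one could. The control value is therefore fixed in advance.

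If section 11.4.4 is followed as written, the report will carry either a p-value that looks like evidence of an effect on new prescribing but only says the intervention-arm count is above zero, or a model that fails to estimate. Neither tells the reader whether residents given the review start more new drugs than residents under usual care.

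**Working it through.** **1. Which participants can score.** The outcome (5.2) requires that the intervention be the cause. The route is review, then propositions, then deprescribing plan (6.1, 8.1.1), and it exists in one arm only. Controls have usual care (6.1, 8.1.2). The control value is zero by definition, whatever drugs controls actually start.

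**2. What is done with the score.** Section 11.4.4 covers all patient-level secondary outcomes. Reading outcome 4 as NH-level does not help, because that route is also a test between allocation groups.

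**3. Whether a derivation changes the reading.** Section 9.2.2 has five subsections: inappropriate DDDs, regular drugs, regular DDDs, EQ-5D-5L and common complaints. These match outcomes 1, 2, 3, 5 and 6. Nothing there covers outcome 4 or gives it a control-arm counterpart.

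**4. How the plan treats counts of the same kind.** Items 1 to 6 of section 5.3 count propositions validated, accepted and implemented. Section 9.2.3.1 says of them: "Those 6 outcomes will be computed from the information provided on the deprescribing plans at baseline and follow-up". As implementation outcomes they are described and not tested. Outcome 4 resembles them but is listed in 5.2, so that exemption does not reach it.

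**5. Number of values affected.** Section 11.2 gives half of 18 NHs, 59 beds on average and 20% recruited: 9 × 59 × 0.20 = 106.2, which reproduces the stated 106. At 1:1 allocation (6.2.1), 106 / 2 = 53 values are fixed at zero. Section 6.1's estimate of 100 gives 50.

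**6. What the comparison returns (illustration only).** Section 11.4.3 names a mixed model but no distribution or link, and the plan states no significance level; two-sided 0.05 is assumed. Let k intervention participants have one new drug each, with 53 per arm.

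*Identity link.* The group estimate is k/53 − 0 = k/53, that is, the intervention-arm mean. An ordinary pooled t-test at k = 4 shows the arithmetic:
- mean = 4/53 = 0.0755
- intervention-arm variance = 0.0755 × 0.9245 × 53/52 = 0.0711; control variance = 0
- pooled variance = 0.0711 / 2 = 0.0356
- standard error = √(0.0356 × 2/53) = 0.0366
- t = 0.0755 / 0.0366 = 2.06 on 104 df, p = 0.042

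The table adds a Gaussian mixed model with a random intercept for nine NHs (its fits gave boundary warnings) and Fisher's exact test on k/53 against 0/53.

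| k | Pooled t | Mixed model, one case per NH | Mixed model, all cases in one NH | Fisher exact |
|---|---|---|---|---|
| 3 | 0.080 | 0.077 | 0.052 | 0.243 |
| 4 | 0.042 | 0.039 | 0.016 | 0.118 |
| 5 | – | – | – | 0.057 |
| 6 | – | – | – | 0.027 |

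The count at which p falls below 0.05 is four under one method and six under another. No threshold can be attributed to the plan.

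*Log link.* With all controls at zero, the likelihood keeps rising as the control rate approaches zero, a value a log link cannot reach. In a Poisson mixed model with an NH random intercept and k = 4, the profile log-likelihood at log rate ratios 0, 2, 4, 8, 16 and 30 is −17.109, −14.844, −14.409, −14.337, −14.33599 and −14.33599. It climbs to a plateau with no finite maximum. The same pattern appears for k = 1, 6 and 10.

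**The case against.** The strongest reply is that section 11.4.2 already deals with this quantity. Its sentence on added drugs nearly repeats the outcome's wording, sits in the statistical chapter, and is more specific than the general sentence in 11.4.4. A reader could fairly conclude that description was always intended and that only a cross-reference is missing. This stands as evidence of intent. It does not settle the matter: the same section says outright that implementation outcomes will not be tested and says nothing similar here, and describing a variable does not remove it from a rule covering all patient-level secondary outcomes.

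It can also be said that the source of the count is evident, since the deprescribing plan is uploaded at both visits (9.3.1, 9.3.2), and that the annexed forms, which are listed but not reproduced, may define it. That is fair. The missing derivation is shown only for the protocol text, and it matters mainly because a derivation could have supplied a control-arm counterpart.

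Three stronger readings are tempting, and the documents do not support them.

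- *Control data are missing.* Section 8.6 says "The interventions other than the ones specified in the deprescribing plan will not be collected", from which a reader might infer that new drugs in controls go unseen. But medication plans are uploaded in both arms at both visits (9.3.1, 9.3.2) and transcribed for each participant (9.2.1). The zero comes from the outcome's wording alone.
- *The statistician's blinding is broken.* One coded group all zero beside a non-zero one would identify the arms. Section 6.2.2 recognises this risk for treatment-change data and puts descriptive statistics after the primary analysis. It sets no timing for outcome 4 as a tested outcome, but nothing says it will be handled first. The primary analysis is exposed only if it is.
- *A handful of drugs guarantees a false positive.* That depends on an identity link the plan does not name. Fisher's test at four gives 0.118, and a log link gives no usable estimate.

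**Conclusion.** The point holds and is minor. Read as written, the plan compares an intervention-arm count with a structural zero. The result would be a statement that the count exceeds zero or, under a log link, no finite estimate. Neither is an effect against usual care.

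This rests on the plain reading of the outcome's wording and on the absence of an exemption in 11.4.4. It does not rest on the illustrative p-values, which depend on assumptions about link, significance level and the spread of cases over NHs.

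The reach is one of six secondary outcomes. The synopsis names mortality, hospitalisation, falls and quality of life as the main ones, so this is not among them. The primary outcome's definition and model are unaffected, as is the change in number of regular drugs (outcome 2), which is countable in both arms.

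**What to change.** Add one sentence to section 11.4.4: outcome 4 is not tested between arms and is reported descriptively for the intervention arm, after the primary analysis, in line with section 6.2.2. A one-line derivation in 9.2.2 naming the deprescribing plan as the source would complete it. This needs no new data and brings the outcome into line with the similar counts in section 5.3.

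If a comparison with usual care is wanted, define a separate arm-neutral count: regular drugs on the 4-month medication plan that are absent from the baseline plan, derived identically in both arms from the plans already uploaded. Section 6.1 places baseline collection before implementation of the deprescribing plan, so the baseline plan can serve; the definition should say so, because 9.3.1 times that visit at implementation. The cost is one derived variable and its definition in 5.2 and 9.2.2. The downsides are that it asks a different question (any new drug, not omissions corrected by the review), includes substitutions, and misses drugs started and stopped between visits.
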